### **9.2 Population pharmacokinetics**

A population PK modeling of the LCM concentration time data will be performed within the NONMEM software. The effects of age, body weight, AED therapy, and other covariates will be evaluated. Simulations will be undertaken for estimating dose adaptations leading to the same exposure as in adults.

The methods will be described in the Data Analysis Plan (DAP) and the results will be reported in a separate modeling report.

### 9.3 Exposure-response

A model-based approach will be used to describe the relationship between LCM and seizure counts data. The PK and pharmacodynamics (PD) data will be combined and exploratory analyses will be conducted to determine if a dose-response relationship can be demonstrated. Additional information will be documented separately in a DAP.

## 10 SAFETY ANALYSES

The following safety variables will be summarized for the SS.

### 10.1 Extent of exposure

All the summaries described below will also be presented for the FAS.

The overall duration of study medication exposure during each of the Titration Period, Maintenance Period and entire Treatment Period (defined in section 3.2.2) will be calculated, as follows:

Titration Period: date of last dose of study medication during the Titration Period minus the date of first dose of study medication plus 1.

Maintenance Period: date of last dose of study medication during the Maintenance Period minus the date of first dose of study medication during the Maintenance Period plus 1.

Entire Treatment Period: date of last dose of study medication during the entire Treatment Period minus the date of first dose of study medication plus 1.

The overall duration of study medication exposure will be summarized for each of the study periods defined above by treatment group, and repeated by treatment group and age group, and by treatment group and weight group using the levels defined in section 4.8.

In addition, the overall duration of study medication exposure will be summarized using the following categories for each of the study periods defined above by treatment group, and repeated by treatment group and age group, and by treatment group and weight group using the levels defined in section 4.8:

Titration Period:  $\leq 2$  weeks,  $>2-\leq 4$  weeks, and  $>4-\leq 6$  weeks.

Maintenance Period:  $\leq 2$  weeks,  $>2-\leq 4$  weeks,  $>4-\leq 6$  weeks,  $>6-\leq 8$  weeks, and  $>8-\leq 10$  weeks.

Entire Treatment Period:  $\leq 2$  weeks,  $>2-\leq 4$  weeks,  $>4-\leq 6$  weeks,  $>6-\leq 8$  weeks,  $>8-\leq 10$  weeks,  $>10-\leq 12$  weeks,  $>12-\leq 14$  weeks, and  $>14-\leq 16$  weeks.

The median total daily dose during the Titration Period, Maintenance Period, and entire Treatment Period will be summarized by treatment group, and repeated by treatment group and age group, and by treatment group and weight group using the levels defined in section 4.8.

In addition, for the Titration Period, the number of back titration steps for each subject (categorized as: 0, 1-3, 4-6, and  $\geq 7$ ), the number of subjects with a dose change together with the number of dose changes during the interval by dose back titration occurred (categorized as:  $< 2\text{mg/kg/day}$ ,  $\geq 2-\text{<}4\text{mg/kg/day}$ ,  $\geq 4-\text{<}6\text{mg/kg/day}$ ,  $\geq 6-\text{<}8\text{mg/kg/day}$ ,  $\geq 8-\text{<}10\text{mg/kg/day}$ ,  $\geq 10-\text{<}12\text{mg/kg/day}$ , and  $>12\text{mg/kg/day}$ ,  $<100\text{mg/day}$ ,  $\geq 100-\text{<}200\text{mg/day}$ ,  $\geq 200-\text{<}300\text{mg/day}$ ,  $\geq 300-\text{<}400\text{mg/day}$ , and  $\geq 400\text{mg/day}$ ), the number of up titration steps for each subject (categorized as: 0, 1-3, 4-6, and  $\geq 7$ ), and the number of subjects with a dose change together

with the number of dose changes during the interval by dose up titration occurred (categorized as: <2mg/kg/day, ≥2-<4mg/kg/day, ≥4-<6mg/kg/day, ≥6-<8mg/kg/day, ≥8-<10mg/kg/day, ≥10-≤12mg/kg/day, and >12mg/kg/day, <100mg/day, ≥100-<200mg/day, ≥200-<300mg/day, ≥300-≤400mg/day, and >400mg/day), will be summarized by treatment group, and repeated by treatment group and age group, and by treatment group and weight group using the levels defined in section 4.8.

## 10.2 Adverse events

AEs will be tabulated by MedDRA SOC and MedDRA PT. The number and percentage of subjects experiencing each event at least once will be summarized. All summaries will be sorted alphabetically by SOC and by frequency of events within PTs, starting with the most frequent event overall.

AEs will be classified as pre-treatment, treatment-emergent, or post-treatment. Pre-treatment AEs are defined as AEs which had an onset date prior to the first study medication administration. Treatment-emergent adverse events (TEAE) are defined as those events which start on or after the date of first study medication administration and within 30 days following the date of last study medication administration, or whose severity worsens within this time frame. Post-treatment AEs are defined as AEs which had an onset date after 30 days after the last study medication administration.

All AEs reported during the study including pre-treatment and post-treatment AEs will be provided in a subject data listing.

An overall summary of AEs will provide the overall summary of TEAEs and the numbers and percentages of subjects with at least 1 TEAE, with a serious TEAE, with a TEAE that led to permanent withdrawal of study medication, with a drug-related TEAE, with a severe TEAE, and with a drug-related serious TEAE. The number and percentage of subject discontinuations due to TEAEs, and the number and percentage of subjects with AEs leading to death (if applicable), will also be summarized. This overall summary will be repeated by treatment group and age group, and by treatment group and weight group using the levels defined in section 4.8.

The following summaries of AEs will be provided for each treatment group by MedDRA primary SOC and PT:

- Incidence of TEAEs
- Incidence of serious TEAEs
- Incidence of TEAEs leading to discontinuation of study medication

All three of these summaries will then be repeated by treatment group and age group, using the levels defined in section 4.8. In addition, all three of these summaries will be repeated including the site and subject number of all those subjects experiencing each TEAE and will be presented by treatment group.

The incidence of TEAEs during the Titration, Maintenance, Transition, Taper, and Safety Follow-Up Periods, separately, will also be presented for each treatment group by MedDRA primary SOC and PT.

The incidence of drug-related TEAEs by seriousness will be presented for each treatment group by MedDRA primary SOC and PT.

The incidence of TEAEs by dose at onset will be presented for each treatment group by MedDRA primary SOC and PT, and will be repeated by treatment group and age group, and by treatment group and weight group using the levels defined in section 4.8.

The incidence of non-serious TEAEs occurring in at least 5% of subjects in any treatment group will be summarized for each treatment group by MedDRA primary SOC and PT, and will be repeated by treatment group and age group, using the levels defined in section 4.8.

Other significant AEs, defined in Appendix 12 (section 12.2), will be summarized for each treatment group by MedDRA primary SOC and PT, and will be repeated by treatment group and weight group, using the levels defined in section 4.8.

In addition, summaries for the incidence of TEAEs overall, incidence of serious TEAEs, incidence of TEAEs leading to discontinuation of study medication, and incidence of other significant TEAEs will be repeated presenting the site and subject number of all those subjects experiencing each TEAE. Subject data listings will also be presented.

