5.1.1 Study duration per subject

Each subject's participation in the study begins with an 8-week Baseline Period. Each subject's total duration of study medication administration is up to 24 weeks; this includes a 6-week Titration Period, a 10-week Maintenance Period, and a 4-week Transition Period (for subjects who plan to enter the open-label extension study [EP0034]) and a Taper Period (2 to 4 weeks, depending on dose level achieved for subjects who will not be entering EP0034). The total study duration can be up to 36 weeks, including the 30-day Safety Follow-Up Period. Both the total duration of study medication and the total study duration include the possibility of a subject who completes the Transition Period choosing not to participate in EP0034 and having to enter the Taper Period.

The end of the study is defined as the date of the last visit of the last subject in the study.

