7.2.3 Transition Period (for subjects who plan to enter EP0034)

At the end of the Maintenance Period (Visit 8), all subjects who complete the Maintenance Period will be offered the opportunity to enroll in an open-label extension study (EP0034). Subjects who plan to enroll in EP0034 will proceed to a 4-week blinded Transition Period.

Subjects randomized to LCM will maintain their Maintenance Period dose throughout the Transition Period. Subjects randomized to placebo will transition in a double-blind fashion to LCM dosing as described Table 7–4. At the completion of the Transition Period, subjects eligible to enter EP0034 will be placed on a common dose (see Figure 5–2) based on body weight category at EP0034 entry.

Table 7-4: Transition Period LCM dosing schedule for subjects randomized to placebo

Body weight category (formulation)	LCM doses for the Transition Period			
	Week 17	Week 18	Week 19	Week 20
<30kg (oral solution)	2mg/kg/day	4mg/kg/day	6mg/kg/day	8mg/kg/day
≥30kg to <50kg (oral solution)	2mg/kg/day	4mg/kg/day	6mg/kg/day	6mg/kg/day
≥50kg (tablets)	100mg/day	200mg/day	300mg/day	300mg/day

LCM=lacosamide

Note: The subject's body weight at Baseline (Visit 2) will be used to determine dose throughout the study.

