7.2.4 Taper Period (for subjects not entering EP0034)

A blinded Taper Period (2 to 4 weeks, depending on dose achieved) will be required for subjects who discontinue study medication prematurely and for subjects who complete the Maintenance Period but choose not to enter the open-label extension study (EP0034).

Table 7-5 provides the taper steps based on the dose of LCM (or matching placebo) achieved. A slow taper is permitted if medically necessary. Whenever possible, these cases should be discussed with the medical monitor prior to withdrawing the subject from the study, especially in cases in which withdrawal criteria have been met. In case of an emergency, a faster taper is permitted after discussion with the medical monitor, whenever possible. Taper of LCM may not be required for some subjects who discontinue study medication prematurely, depending on the treatment option selected by the investigator in consultation with the subject and/or parent/legal representative.

Table 7–5: Taper Period dosing of LCM (or matching placebo)

LCM (or matching placebo) dose achieved	LCM (or matching placebo) doses for the Taper Period			
	Week 17	Week 18	Week 19	Week 20
11 or 12mg/kg/day	9mg/kg/day	6mg/kg/day	4mg/kg/day	2mg/kg/day
9 or 10mg/kg/day	8mg/kg/day	6mg/kg/day	4mg/kg/day	2mg/kg/day
7 or 8mg/kg/day	6mg/kg/day	4mg/kg/day	2mg/kg/day	2mg/kg/day
5 or 6mg/kg/day	4mg/kg/day	2mg/kg/day	2mg/kg/day	NA
3 or 4mg/kg/day	2mg/kg/day	2mg/kg/day	NA	NA
2mg/kg/day	NA	NA	NA	NA
350 or 400mg/day	300mg/day	200mg/day	100mg/day	100mg/day
250 or 300 mg/day	200mg/day	100mg/day	100mg/day	NA
150 or 200mg/day	100mg/day	100mg/day	NA	NA
100mg/day	NA	NA	NA	NA

LCM=lacosamide; NA=not applicable (taper not required)

Note: The oral solution is dosed as mg/kg/day and tablets are dosed as mg/day.

Note: Subjects not requiring taper will enter directly into the Safety Follow-Up Period and not attend any Taper Period visits.

Note: The subject's body weight at Baseline (Visit 2) will be used to determine dose throughout the study.

Note: The study week numbers provided are for subjects who complete the Maintenance Period and enter the Taper Period. The study week numbers provided do not apply to subjects who enter the Taper Period at other times.

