## **3.2 General study level definitions**

### **3.2.1 Analysis time points**

#### **3.2.1.1 Last dose of study medication**

Unless otherwise noted, all references to the last dose of study medication in this SAP refer to the last dose of study medication taken across all study periods (ie, the last dose of study medication across the Titration, Maintenance, Transition, and Taper Periods). The last dose of study medication during the Treatment Period will be defined as the last dose during the Titration and Maintenance Periods.

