#### Taper Period

For those subjects who discontinue study medication or for those subjects who complete the Maintenance Period but choose not to enter EP0034, the Taper Period is defined as the date after the last dose of study medication in the Titration, Maintenance or Transition Periods, as appropriate, and the date of last dose of study medication.

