## **3.6 Treatment assignment and treatment groups**

It is expected that subjects will receive treatment as randomized. Thus, treatment assignment for the FAS and the SS will be according to randomization. However, if after unblinding it is determined that the subjects received treatment other than what they were randomized to receive, the safety analyses will be conducted using treatment assignments according to the actual treatment received (SS-as treated).

All subjects treated in this study receive study LCM at doses ranging from 8mg/kg/day to 12mg/kg/day (oral solution) for subjects weighing <30kg, 6mg/kg/day to 8mg/kg/day (oral solution) for subjects weighing  $\geq$ 30kg to <50kg, 300mg/day to 400mg/day (tablets) for subjects weighing  $\geq$ 50kg, or matching placebo. The subject's body weight at Baseline (Visit 2) will be used to determine dose throughout the study. Summaries will be presented based on treatment group; Placebo and LCM, and will generally not be differentiated by LCM dose. Where appropriate, LCM dose will be presented in subject data listings.

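### Most TEAE tables count events that begin while placebo-randomised subjects are taking LCM under Placebo, and no TEAE table pools the placebo-controlled Treatment Period

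*SAP*

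**What the plan says.** - **Window.** SAP 10.2 counts as treatment-emergent any event that "start on or after the date of first study medication administration and within 30 days following the date of last study medication administration", or that worsens in that window. Protocol 13.4.1 uses the same window.
- **Last dose.** SAP 3.2.1.1 sets a default rule that "all references to the last dose of study medication in this SAP refer to the last dose of study medication taken across all study periods", that is, Titration, Maintenance, Transition and Taper. SAP 10.2 notes no exception.
- **Columns.** SAP 3.6 states that "treatment assignment for the FAS and the SS will be according to randomization", with two groups, Placebo and LCM. The as-treated alternative for safety applies only "if after unblinding it is determined that the subjects received treatment other than what they were randomized to receive".
- **Transition.** Protocol 7.2.3: "Subjects randomized to placebo will transition in a double-blind fashion to LCM dosing". Table 7-4 gives the LCM doses for Weeks 17 to 20.
- **Taper.** Protocol 5.1.1 allows for "the possibility of a subject who completes the Transition Period choosing not to participate in EP0034 and having to enter the Taper Period". Table 7-5 "provides the taper steps based on the dose of LCM (or matching placebo) achieved". SAP 3.2.2 accordingly starts the Taper Period at "the date after the last dose of study medication in the Titration, Maintenance or Transition Periods, as appropriate".
- **TEAE tables.** SAP 10.2 plans an overall summary (repeated by age and by weight); all, serious and leading-to-discontinuation TEAEs (each repeated by age); drug-related TEAEs by seriousness; non-serious TEAEs in at least 5% (repeated by age); other significant AEs (repeated by weight); and a dose-at-onset table. Only the all-TEAE incidence is also split into Titration, Maintenance, Transition, Taper and Safety Follow-Up, each shown on its own.

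**The concern.** For placebo-randomised subjects who continue towards EP0034, the TEAE window runs on into time on LCM while the column heading stays Placebo. In the tables without a period split, Placebo is then not a placebo-only column, and the contrast with LCM is not the placebo-controlled one.

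AEs and withdrawals due to AEs are the primary safety variables (SAP 2.2.2.1), and a reader will go to these tables for the comparison. The rest of the safety plan is handled differently: the abnormality definitions for laboratory values (SAP 10.3), vital signs (10.4.1) and ECGs (10.4.2), and the exposure summaries (10.1), all stop at the end of the Treatment Period. The AE tables therefore cover time on LCM that the exposure tables do not describe.

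**Working it through.** **1. Does the as-treated rule remove the problem?** No. It deals with subjects found after unblinding to have received something other than their allocation. LCM in Transition is the planned course of the placebo arm, and the rule does not reassign events by period.

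**2. Dosing time.** Inputs are Protocol 5.1.1 and Tables 7-4 and 7-5. The protocol's 24-week maximum reproduces: 6 (Titration) + 10 (Maintenance) + 4 (Transition) + 4 (longest Taper) = 24. The LCM share of a placebo-randomised subject's dosing weeks is (LCM weeks)/(16 + LCM weeks):

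| Course after Week 16 | LCM weeks | Share |
|---|---|---|
| Transition completed, enters EP0034 | 4 | 4/20 = 20% |
| Transition, then Taper, <30kg (Week 20 dose 8mg/kg/day, 4 taper weeks) | 8 | 8/24 = 33% |
| Transition, then Taper, heavier categories (6mg/kg/day or 300mg/day, 3 taper weeks) | 7 | 7/23 = 30% |

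For a subject who takes no LCM, or in a table limited to Titration + Maintenance, the share is 0%. The 30 days after the last dose come on top.

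**3. How many subjects.** SAP 2.4 plans 154 per arm with 14% dropout. If every completer chose EP0034, about 154 × 0.86 = 132 placebo subjects would enter Transition. If 60% of the arm did, the number would be 154 × 0.60 = 92. These are planning figures, not bounds. Each subject whose only such event begins on LCM moves the Placebo percentage by 1/154 = 0.65 points.

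**4. Direction, on assumed rates.** The documents give no AE rates, so every rate here is an assumption, and only Transition onsets are counted. Let e be the share entering Transition, q the new-onset risk in former placebo subjects and c the risk on continued LCM, with Treatment Period incidence 5% (Placebo) and 20% (LCM), a gap of 15.0 points.

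Placebo = 0.05 + 0.95·e·q; LCM = 0.20 + 0.80·e·c.

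| q | c | e | Placebo | LCM | Gap (points) |
|---|---|---|---|---|---|
| 2% | 1% | 0.60 | 6.14% | 20.48% | 14.3 |
| 5% | 1% | 0.86 | 9.09% | 20.69% | 11.6 |
| 2% | 2% | 0.60 | 6.14% | 20.96% | 14.8 |
| 2% | 2% | 0.86 | 6.63% | 21.38% | 14.7 |
| 2% | 5% | 0.60 | 6.14% | 22.40% | 16.3 |
| 2% | 5% | 0.86 | 6.63% | 23.44% | 16.8 |

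The gap narrows only if q > (0.80/0.95)c = 0.84c; otherwise it stays the same or widens.

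**5. Can the planned by-period tables be combined?** No. One subject may have the same preferred term in Titration and in Maintenance, so the two incidences do not add to a Treatment Period incidence. In the Taper and Safety Follow-Up tables, the Placebo column can itself mix subjects who never took LCM with subjects coming off it after Transition.

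**The case against.** The strongest reply is that much of the information is already planned, and this stands in part:

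- The separate Titration and Maintenance tables are fully placebo-controlled, and Transition has its own table.
- Disposition by period (SAP 5.1) gives reasons for discontinuation, so Treatment Period counts of withdrawals due to AEs can be added up.
- Serious, discontinuation and other significant TEAEs are repeated with subject numbers, and all AEs are listed, so events could be traced to a period by hand.
- The dose-at-onset table may separate events on LCM, although the SAP does not say how dose is classed for placebo subjects.

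These do not replace a pooled comparison. The period split covers only all TEAEs, and tracing events through listings is not a planned summary.

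It is also fair that the SAP follows the protocol's window, that safety is descriptive (Protocol 13.4), so no test is affected, and that no direction of bias is shown. The size figures are soft: 154 is 135 × 1.14 = 153.9, so the plan's own evaluable number is 135 per arm, not 132. The 30% and 33% shares apply only to subjects who complete Transition and then decline EP0034, whose number is not given.

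Finally, the request is not trivial. Keeping every existing age and weight repeat means 14 further tables (overall 3; all, serious and discontinuation 2 each; drug-related 1; non-serious 2; other significant 2), or 18 with the four subject-number repeats.

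**Conclusion.** The concern holds and should be fixed. Followed exactly, the SAP places events that begin on LCM in the Placebo column of every TEAE table that is not split by period, and plans no TEAE table for Titration and Maintenance together. A placebo subject who completes Transition contributes 20% of dosing weeks on LCM, or 30% to 33% if LCM is then tapered; these shares follow from the documents. The change in any between-arm difference cannot be stated: on the assumed rates above, a 15.0-point gap becomes anything from 11.6 to 16.8. The case for change is that the comparison is not the placebo-controlled one, not that it is biased in a known direction.

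**What to change.** In SAP 10.2:

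1. Keep the all-period tables that the protocol defines, with a footnote that the Placebo column includes events beginning on LCM.
2. Add Treatment Period versions (onset or worsening in Titration + Maintenance, using the SAP 3.2.2 definition) of the overall summary and of the all-TEAE, serious, leading-to-discontinuation, drug-related, non-serious ≥5% and other significant tables, with their existing repeats. Name these as the between-arm comparison.
3. Show Transition events, and Taper and Safety Follow-Up events of subjects who entered Transition, under placebo-to-LCM and LCM-to-LCM headings.
4. State how dose is classed for placebo subjects in the dose-at-onset table.

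Cost: one derived period flag, one entered-Transition flag, the additional tables and a footnote. There is no new data collection and no effect on conduct. The drawback is that the Treatment Period ends at the Early Termination Visit for early discontinuers, so the new tables omit those subjects' taper and follow-up events. The all-period tables retain them, which is why both sets are needed.

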7.2.1 Titration Period

Table 7-1 provides the recommended LCM (or matching placebo) dosing during the Titration Period for subjects to reach the target doses for the Maintenance Period. All subjects are required to complete Week 1 study medication dosing before dosing flexibility is allowed based on tolerability.

Table 7–1: Recommended dosing schedule for LCM (or matching placebo) during the Titration Period

Body weight category (formulation)	Target LCM (or matching placebo) doses for the Titration Period					
	Week 1 ^a	Week 2	Week 3	Week 4	Week 5	Week 6
<30kg (oral solution)	2mg/kg/day	4mg/kg/day	6mg/kg/day	8mg/kg/day	10mg/kg/day	12mg/kg/day
≥30kg to <50kg (oral solution)	2mg/kg/day	4mg/kg/day	6mg/kg/day	8mg/kg/day	8mg/kg/day	8mg/kg/day
≥50kg (tablets)	100mg/day	200mg/day	300mg/day	400mg/day	400mg/day	400mg/day

LCM=lacosamide

Note: Subjects may not receive doses higher than LCM 12mg/kg/day (body weight <30kg), LCM 8mg/kg/day (body weight ≥30kg to <50kg), or LCM 400mg/day (body weight ≥50kg), or matching placebo.

Note: The subject's body weight at Baseline (Visit 2) will be used to determine dose throughout the study.

^a All subjects are required to complete Week 1 study medication dosing before dosing flexibility is allowed based on tolerability. Subjects who are unable to complete the Titration Period or subjects who will not be able to attain at least the minimum Maintenance Period target dose, should be withdrawn and enter the Taper Period.

After completion of Week 1, investigators will assess whether a subject would tolerate a further dose increase or whether a subject should hold the Week 1 dose for a longer duration. This hold will be at the investigator's discretion.

Table 7–2 provides LCM (or matching placebo) dosing with flexibility based on tolerability during the Titration Period.

Table 7–2: Dosing of LCM (or matching placebo) with flexibility based on tolerability during the Titration Period

Body weight category (formulation)	Target LCM (or matching placebo) dose increase/week ^a (titration)	LCM (or matching placebo) dose decrease per back titration step		Subsequent LCM (or matching placebo) dose increase ^b (dose increase after back titration step)	
		Min	Max	Min	Max
<30kg (oral solution)	2mg/kg/day	1mg/kg/day	2mg/kg/day	1mg/kg/day	2mg/kg/day
≥30kg to <50kg (oral solution)					
≥50kg (tablets)	100mg/day	50mg/day	100mg/day	50mg/day	100mg/day

LCM=lacosamide; Max=maximum; Min=minimum

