Note: Asymmetrical dosing with no more than 50mg difference between morning and evening doses will be allowed for subjects taking tablets who require back titration in a 50mg increment (ie, only 50mg and 100mg tablets are available).

Note: The subject's body weight at Baseline (Visit 2) will be used to determine dose throughout the study.

^a Titration step to achieve a dose not previously administered

^b Titration step subsequent to a back titration

There is no limit to the number of back titration steps or dose holds allowed and all are at the investigator's discretion; however, subjects must achieve the minimum LCM (or matching placebo) target dose for their body weight category by the end of the Titration Period. If it becomes apparent that a subject will not be able to reach the minimum target dose, then the subject should be withdrawn from the Titration Period and enter the Taper Period.

Subjects who have their study medication titrated to a higher dose not previously administered should remain at that dose for ≥7 days unless a back titration step is required based on tolerability. Subjects who have their study medication back titrated must remain on the lower dose for ≥3 days (in order to reach steady state) before a subsequent dose increase. After back titration, subjects who return to a higher dose previously administered must maintain that dose for ≥3 days before subsequent titration to a higher dose.

As outlined in Table 7–3, subjects will be required to achieve and maintain at least a minimum LCM (or matching placebo) dose for at least the final 3 days of Week 6 to be eligible for entry into the Maintenance Period. Subjects may have a back titration step as late as the last day of Week 6, as long as the minimum target dose is maintained.

Table 7–3: Required LCM (or matching placebo) dose for at least the final 3 days of Week 6

Body weight category (formulation)	LCM (or matching placebo) dose for at least the final 3 days of Week 6	
	Min	Max
<30kg (oral solution)	8mg/kg/day	12mg/kg/day
≥30kg to <50kg (oral solution)	6mg/kg/day	8mg/kg/day
≥50kg (tablets)	300mg/day	400mg/day

LCM=lacosamide; Max=maximum; Min=minimum

Note: The subject's body weight at Baseline (Visit 2) will be used to determine dose throughout the study.

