7.2.2 Maintenance Period

Subjects who reach and maintain at least the minimum study medication dose for at least the final 3 days of the Titration Period, will enter a 10-week Maintenance Period at the dose they received on the final day of the Titration Period (Table 7–3). Lacosamide (or matching placebo) doses will remain stable throughout the Maintenance Period. Subjects who require a change in dose during the Maintenance Period will be withdrawn from the Maintenance Period and enter the Taper Period. Taper of LCM may not be required for some subjects who discontinue study medication prematurely, depending on the treatment option selected by the investigator in consultation with the subject and/or parent/legal representative.

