## 3 DATA ANALYSIS CONSIDERATIONS

### 3.1 General presentation of summaries and analyses

Statistical analysis and generation of tables, figures, subject data listings, and statistical output will be performed using SAS Version 9.3. All tables and listings will use Courier New font size 9.

Descriptive statistics will be displayed to provide an overview of the study results. For categorical parameters, the number and percentage of subjects in each category will be presented. The denominator for percentages will be based on the number of subjects appropriate for the purpose of analysis. Unless otherwise noted, all percentages will be displayed to 1 decimal place. No percentage will be displayed for zero counts, and no decimal will be presented when the percentage is 100%. For continuous parameters, descriptive statistics will include number of subjects (n), mean, standard deviation (SD), median, minimum, and maximum.

Decimal places for descriptive statistics will always apply the following rules:

- “n” will be an integer.
- Mean, SD, and median will use 1 additional decimal place compared to the original data.
- Coefficient of variance (CV[%]) will be presented with 1 decimal place.
- Minimum and maximum will have the same number of decimal places as the original value.

Statistical tests of efficacy variables will be presented as 2-sided p-values rounded to 4 decimal places. P-values less than 0.0001 will be presented as “<0.0001” and p-values greater than 0.9999 will be presented as “>0.9999.” Statistical comparison will be performed at the 0.0500 level of significance.

A complete set of data listings containing all documented data and all calculated data (eg, change from Baseline) will be generated, and will be sorted by site, subject number and visit (where applicable).

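### The table of TEAE incidence by dose at onset takes no account of time at each dose, so within an arm and weight band the final-dose column can look higher with no dose effect

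*SAP*

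**What the plan says.** SAP 10.2 plans the table as follows: "The incidence of TEAEs by dose at onset will be presented for each treatment group by MedDRA primary SOC and PT". It is repeated by age group and by weight group. The measure is set earlier in the same section: "The number and percentage of subjects experiencing each event at least once will be summarized".

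No dose categories, subject-time, period limit or rule for onsets after the last dose is given for this table. On denominators only the general rule in SAP 3.1 applies: "The denominator for percentages will be based on the number of subjects appropriate for the purpose of analysis". By contrast, SAP 10.3 names the denominator for laboratory abnormalities explicitly.

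Time at dose is set by the protocol. Table 7-1 raises the dose weekly. Section 7.2.1 adds: "Subjects who have their study medication titrated to a higher dose not previously administered should remain at that dose for ≥7 days", unless back titration is needed, and puts no limit on holds or back titration steps. Section 7.2.2 then fixes the dose for 10 weeks: "Lacosamide (or matching placebo) doses will remain stable throughout the Maintenance Period".

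SAP 10.1 summarises exposure duration by study period and counts titration steps. It does not summarise time at each dose level.

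**The concern.** A crude percentage grows with the time over which events can start. If one column covers a week and the next covers most of the study, comparing them within an arm compares durations as well as doses.

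SAP 3.6 says summaries will generally not be split by lacosamide dose, so this is the TEAE table a reader will turn to for dose. The protocol's introduction reports a dose relationship in adults for dizziness, nausea and diplopia, so a rising pattern could be taken as confirmation.

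The distortion can also run the other way. If weekly risk were 10% at the starting dose and 2% later (both assumed), the table would show 1 − exp(−0.10) = 9.5% for the 1-week starting dose and 19.7% for an 11-week final dose. A five-fold higher weekly risk would then appear as less than half.

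No planned exposure summary lets a reader undo this.

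**Working it through.** **Time at each dose (Table 7-1 plus 10 weeks of Maintenance)**

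- <30kg: 2, 4, 6, 8 and 10mg/kg/day for 1 week each, then 12mg/kg/day for 1 + 10 = 11 weeks. Total 5 + 11 = 16 weeks.
- ≥30kg to <50kg: 2, 4 and 6mg/kg/day for 1 week each, then 8mg/kg/day for 3 + 10 = 13 weeks. Total 3 + 13 = 16 weeks.
- ≥50kg: 100, 200 and 300mg/day for 1 week each, then 400mg/day for 13 weeks. Total 16 weeks.

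Each total reproduces the protocol's 16-week Treatment Period. The final dose takes 11/16 = 69% or 13/16 = 81% of it.

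**Variation around the schedule.** Back titration on the last day of Week 6 leaves about 10 weeks at the final dose. Transition adds 4 weeks for lacosamide subjects, giving 15 or 17. Taper adds low-dose weeks: from 8mg/kg/day, one week each at 6 and 4 and two at 2mg/kg/day (Table 7-5).

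**Constant weekly risk h, no dose effect.** Incidence over w weeks = 1 − exp(−hw). The documents give no TEAE rates, so h is assumed. With h = 0.02:

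- 1 week: 1 − exp(−0.02) = 2.0%
- 11 weeks: 1 − exp(−0.22) = 19.7%, ratio 10.0
- 13 weeks: 1 − exp(−0.26) = 22.9%, ratio 11.6

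For h from 0.10 down to 0.005, the ratio runs from 7.0 to 10.7 (11 weeks) and from 7.6 to 12.6 (13 weeks). If only a subject's first onset counts, at h = 0.02 the final dose shows exp(−0.10) − exp(−0.32) = 17.9% or exp(−0.06) − exp(−0.32) = 21.6%, against 2.0% in Week 1.

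**Risk concentrated in the first week at each new dose, no dose effect.** Later h = 0.005 (assumed).

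- First week 10 times higher (0.05): 1 week, 1 − exp(−0.05) = 4.88%. At 11 weeks, 1 − exp(−(0.05 + 10 × 0.005)) = 9.52%, ratio 1.95. At 13 weeks, 1 − exp(−(0.05 + 12 × 0.005)) = 10.42%, ratio 2.14.
- First week 20 times higher (0.10): 9.52%, 13.93% and 14.79%, ratios 1.46 and 1.55.

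**Across weight bands.** The 8mg/kg/day dose is a 1-week step below 30kg and the 13-week final dose at ≥30kg to <50kg. At h = 0.02 the same nominal dose shows 2.0% in one band and 22.9% in the other.

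**The case against.** The strongest case against has five parts.

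- **Shape of risk.** The 10- to 12-fold figure needs a constant weekly risk. The design allows holds and back titration precisely because tolerability problems are expected when the dose rises. If onsets cluster there, the ratio is about 1.5 to 2. This stands. Withdrawal or back titration of intolerant subjects before the top dose also works in the opposite direction.
- **Pooled columns.** A reader might infer a steady rise with dose in the overall table. The schedule does not support that. Under constant risk the mg/kg columns would be low at 2, 4 and 6, high at 8, low at 10 and high at 12. The gradient belongs within a weight band.
- **Denominator.** A reader might infer that subjects exposed at each dose will not be the denominator. The SAP does not say so; its general rule permits that choice. The accurate statement is that the denominator is unspecified. Using subjects exposed would correct for how many reached the dose, but not for how long they stayed.
- **Other tables.** Placebo subjects follow the same nominal steps through Week 16, so a pure time artefact would appear in both arms. TEAEs are also tabulated by study period. Both help in part. However, the TEAE window runs to 30 days after the last dose, and placebo subjects who enter Transition receive active lacosamide (Table 7-4). Without a period limit, low-dose columns in the placebo arm could mix placebo and active drug. The Titration table pools the lower doses with 1 to 3 weeks at the final dose.
- **Consequence.** The table is descriptive, dose is not randomised, and no test or dose-response conclusion is attached. This stands and limits the weight of the point.

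**Conclusion.** The point holds in a bounded form. As specified, the table confounds dose with time at dose for comparisons within an arm and weight band, and it mixes very different durations in the pooled 8mg/kg/day column. With no dose effect, the final-dose column could be about 10 to 12 times a 1-week column at a constant 2% weekly risk, or about 1.5 to 2 times if risk is concentrated after each dose increase. Both figures rest on assumed risks and on the recommended schedule through Week 16.

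It would go too far to say that the table will show a false dose-response. The documents give no event rates, and the result depends on how onsets cluster and on who reaches the top dose. Comparing lacosamide with placebo at the same nominal dose remains a partial check if confined to the Treatment Period. The primary efficacy analysis is unaffected. This is a cheap improvement to a descriptive safety table.

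**What to change.** In SAP 10.2:

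- Limit the table to the Treatment Period. Show onsets in Transition, in Taper and off drug separately.
- For each nominal dose and arm, within weight band, give the number of subjects exposed at that dose (as the denominator), subject-weeks at that dose, and onsets per 100 subject-weeks. Under a constant 2% weekly risk, every dose would then show about 2 per 100.
- Optionally, add incidence in the first 7 days at each dose among subjects who reached it. This is useful if onsets cluster: in the 10-times scenario above, the average weekly risk over 11 weeks is (0.05 + 10 × 0.005)/11 = 0.91 per 100 subject-weeks against 5.0 in a 1-week column, so subject-time alone could then understate the final dose.
- Footnote that dose is not randomised and is confounded with time and with tolerance of earlier doses.

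The cost is SAP wording and programming. No new data are needed, because the compliance calculation in SAP 7 already uses morning and evening doses for each day. The 1-week cells will be imprecise. If the planned 154 subjects per arm split evenly over three weight bands (assumed), a cell holds 154/3 ≈ 51 subject-weeks, or 51 × 0.02 ≈ 1 onset at 2% weekly. The first-7-day figures also select subjects who tolerated the lower doses.
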